Biomarkers of the RIC treatment is a new area of stroke research and are important to establish in order to assess and predict responders of the conditioning treatment. Rheo-erythrocyte dysfunction of the Red Blood Cell (RBC) is a novel biomarker in both ischemic strokes in general and on the effect of RIC. Red Blood Cells with a diameter of 6-8 μm must be highly deformable in order to deliver oxygen to brain tissue by travelling through micro vessels with a diameter of just 2-3 μm . RBC's can carry nitric oxide as NO₂-/s-nitrosylated proteins. These proteins improve RBC deformability and induce hypoxic vasodilation thereby improving passage through the microvasculature(13-18). RBC's also express Erythrocyte Nitric Oxide Synthase 3, which regulate the rheo-erythrocyte function. Erythrocyte Nitric Oxide Synthase 3 is activated by shear stress and provide an extra source of NO for hypoxic vasodilation(19-22). Preliminary data have shown that experimental stroke on mice seems to cause a rheo-erythrocyte dysfunction of the RBC's leading to a loss of deformability. The RBC's become rigid, which can lead to occlusion of micro vessels in the brain and further ischemic damage. Loss of deformability can be measured as a reduced Elongation Index (EI) by ektacytometry and may be attenuated by RIC(23).

2. Project thesis

Hypothesis

RIC improves rheo-erythrocyte dysfunction in acute ischemic stroke as compared to sham RIC.

Primary endpoint

Rheo-erythrocyte dysfunction in RBC's (deformability and Erythrocyte Nitric Oxide Synthase 3) will serve as a biomarker of the conditioning response and predictor of the clinical outcome in stroke patients.

Secondary endpoints

- RBC deformability presentation across stroke subtypes
- RBC deformability in relation to infarct size/stroke severity
- RBC erythrocrine dysfunction presentation across stroke subtypes
- RBC erythrocrine dysfunction in relation to infarct size/stroke severity
- Difference in 7 days cognitive impairment between treatment groups.
- RBC erythrocrine dysfunction and deformability as a marker for difference in 7 days cognitive impairment
- Circulating microRNA and/or extracellular vesicle profile of RIC-induced neuroprotection
- Circulating microRNA and/or extracellular vesicle profile as a marker for difference in 7 days cognitive impairment
- Circulating microRNA and/or extracellular vesicle profile as a marker for RBC erythrocrine dysfunction and deformability

3. Methods

Design

Pilot, randomized, patient-assessor blinded, sham-controlled study on stroke patients admitted to the Stroke Unit at Aarhus University Hospital.

Patient selection

The study population is selected according to the criteria in table 1:

Table 1. Inclusion and exclusion criteria for stroke patients and controls

Stroke patients Inclusion/Exclusion criteria	
Inclusion criteria	Exclusion criteria
Onset to randomization < 48h Age 18-80 Independent in daily living (mRS 0-2) Legal competent Ambulatory Documented ischemic stroke on baseline MRI	Prior stroke, dementia or other known neurological condition Pregnancy* Contraindications to MRI Investigators discretion Known upper extremity peripheral arterial stenosis Diabetes

Controls Inclusion/Exclusion criteria	
Inclusion criteria	Exclusion criteria
Independent in daily living (mRS 0-2) Ambulatory Age 18-80 Legal competent Non vascular diagnosis (e.g. epilepsy, migraine etc.)	Prior stroke, dementia or other known neurological condition Pregnancy* Contraindications to MRI Investigators discretion Known upper extremity peripheral arterial stenosis Diabetes

**Women of child-bearing age will be asked about their use of safe birth control methods (contraceptive pill, intrauterine devices both hormonal and non-hormonal, hormonal implants, hormonal depot injection and transdermal hormonal patch). A safe birth control method shall be used throughout the study period. A pregnancy test will be performed (ruling out pregnancy) on women of child-bearing age before study participation is possible.*

Informed consent

Patients who fulfill the study criteria will be invited to participate in the study. It will be endeavored to create a calm and safe environment for this conversation either in the patient room or in an interview room at the ward. We will prioritize the presence of nearest relatives at the time of study information and inclusion. Furthermore, we will inform the patient on the right to 24-hour consideration time before entering the study. All information will be given orally as well as in writing. A patient can only participate in the study if he/she has signed the consent forms ("*samtykkeerklæring og fuldmættserklæring*")

A patient can withdraw from the study at any time. Withdrawal can also be due to the principal investigator's discretion. In case the patient cannot be reached by telephone, every effort will be made to contact the patient or to document the outcome regarding new vascular events via registries/electronic health records. If the patient withdraws from the study, the date and the reason for the patient's withdrawal will be recorded. The patient is encouraged to provide information about his or her reason(s) for withdrawal and any experienced adverse effects (AE) during the study.

The study will follow the course of the flow chart (please refer to appendix 2). A total of 45 patients will be included in the study: 15 will receive stroke-RIC, 15 will receive sham-RIC and 15 will constitute the control group. The initial RIC treatment regime will be applied as soon as possible and less than 48 hours after stroke onset. If patients are discharged from the Stroke Unit before day 7, they will continue the RIC treatment at home according to written instructions. On day 7 patients will return to the Stroke Unit for further tests (Table 2 – study procedures) and return the RIC device. The control group will consist of patients with putative stroke/TIA's ending up with a non-vascular diagnosis upon examination in the outpatient clinic or at the stroke unit. In addition to the study procedures all patients will receive standard treatment.

Method of blinding

Patients and the assessors of endpoints are blinded. No information regarding randomization status will be recorded in the patient record.

Discontinuation of study participation

A patient can withdraw from the study at any time. Patients can be withdrawn from the study at the principal investigator's discretion. If the patient withdraws from the study, the date and the reason for the patient's withdrawal will be recorded. The patient is encouraged to provide information about his or her reason(s) for withdrawal and any experienced adverse effects (AE) during the study.

Time schedule

The study is scheduled to start 1st of February 2020 and end upon 31st of January 2021. The inclusion period is scheduled to 5 months.

4. Study procedures and assessment

Baseline data (demographics) and process indicators are collected from the Danish Stroke Registry (DSR). Additional information regarding medical history, treatment characteristics, use of medication, clinical and physiological data during the hospitalization will be obtained from the electronic health records. This includes information about clinical examinations, scan results and biochemical results. Data are recorded in an electronic case report form (CRF) at discharge from the stroke unit. For a complete list of registered data, see *Appendix 1*.

Table 2. Study procedures for patients with acute ischemic stroke.

	Enrollment	Pre-allocation	Post-allocation			Follow-up
Time points			0h	+2h*	Day 0-7 (8AM and PM)	+7days
Informed consent	X					
Randomisation		X				
Intervention						
Remote Ischemic Conditioning (RIC/Sham)			X		X ——— X	
Blood samples						
Blood samples (2x3,0 mL EDTA + 2x3,5 mL citrate)		X		X		X
RBC deformability		X		X		
RBC erythrocyte dysfunction		X		X		X
Biobank samples (EVs and microRNA)		X		X		X
Clinical evaluation						
NIHSS		X				X
PASE questionnaire		X				
MoCA		X				X
RIC questionnaire						X
End of study						X

RIC: Remote Ischemic Conditioning. NIHSS: National Institute of Health Stroke Scale. PASE: Physical Activity scale for the elderly. RBC: Red Blood Cells. EVs: Extracellular Vesicles. microRNA: Micro ribonucleic acid. For patients without a vascular diagnosis study participation will exclude RIC/Sham-RIC treatment and no RIC questionnaire.

*2hours after completion of first RIC/Sham-RIC treatment

Blood samples

Study blood samples will be drawn at the ward in a total of 3 times (Table 2 - Study procedures). Each sample set will consist of 2x3,0 mL EDTA + 2x3,5 mL citrate. Ektacytometry and flowcytometry will be performed on fresh whole-blood samples, excess material (plasma) will be placed in a research biobank and used for nitrite and EV/microRNA analysis. Furthermore, we will use biochemical lab results taken as part of routine care at admission.

Analysis of blood samples will be performed during the study and until 2 years after inclusion of the last patient (no later than 31st of January 2023). After the last analysis and no later than 31st of January 2023 the blood samples will be destroyed.

If routine blood samples are taken, we will endeavor to include the baseline study blood samples in these in order to minimize discomfort for the patient. If, however, the routine blood samples cannot be drawn within less than 2 hours after inclusion, the study personnel will draw them. The blood samples will be safely stored at Aarhus University Hospital. No samples or biological material will be sent abroad. Research documents are stored for 15 years, after which they are destroyed

Blood samples	Accepted time frame
Baseline samples	< 2 hours from inclusion
+2-hour samples	1-3 hours from completed baseline RIC
+7 days samples	< 4 hours from completed 08 AM RIC

Intervention (Remote Ischemic Conditioning)

The investigational device used to induce RIC is an automatic Remote Ischemic Conditioning device (Stroke-RIC) – a blood pressure cuff for application on an upper arm. It is preprogrammed for 5 cycles of RIC. Each of these rounds consist of 5 minutes of inflation followed by 5 minutes of deflation. For the RIC device cuff pressure will be 200 mmHg unless the systolic blood pressure exceeds 175 mmHg in which case a pressure of 35mmHg will be added to the systolic pressure.

Patients allocated to the sham-RIC group will go through the same program as the intervention group, except the sham-RIC device cuff pressure will be only 20 mmHg during inflation.

The devices are designed and developed in corporation with Aarhus University, The faculty of Biomedicine technologies, 8200, Aarhus N, Denmark, Seagull Aps, 4160, Herlufmagle, Denmark and the department of Neurology, Aarhus University Hospital, 8000-DK, Aarhus C.

RIC/sham-RIC protocol	Accepted time frame
Baseline RIC	< 2 hours from inclusion
RIC twice daily for 7 days – 08.00 PM and AM	06.00 to 10.00 PM and 06.00 to 10.00 AM

RBC – deformability - Ectacytometry

The rheological properties of RBCs are quantified using a Deformability or Elongation Index (DI or EI). A higher EI at the optimum viscosity (300 Osmolality) indicates highly deformable RBCs indicative of better microcirculation, while a lower EI indicates rigid RBC's. Briefly, 6 uL of heparinized or EDTA treated fresh blood is mixed with 600-uL of polyvinylpyrrolidone (PVP) solution (300 Osm) and transferred to a disposable kit. The kit is placed inside the laser-assisted

ectacytometer for automated read out, data and image collection as per the vendors instructions. In a similar approach aggregation and shear stress will be measured using 0,5 mL of blood. With the current knowledge on RBC deformability it is impossible to predict a risk of developing specific diseases in the future.

Erythrocrine dysfunction - Flow Cytometry

Analytical flow cytometry for Erythrocyte Nitric Oxide Synthase 3 phosphorylation (pNOS3Ser1177) and s-nitrosylation (-SNO) in RBCs: Red blood cells are separated from 50-uL of freshly fixed blood samples, using a cocktail of monoclonal antibodies to RBC-specific markers (Glycophorin A (GPA)) and Hemoglobin. To assess the functional features, after fixation and permeabilization, RBCs are incubated with antibodies conjugated to fluorochrome either directly or through secondary antibodies to s-nitrosocysteine (-SNO), pNOS3Ser1177 and AMPK α 1. A titration study is currently ongoing to determine the optimal antibody concentration. Next, RBC samples are run through a flow cytometer (Cytoflex S, Beckman Coulter, Colorado, USA), and data is collected using CellQuest software to process for FC analysis. With the current knowledge on the Erythrocrine dysfunction it is impossible to predict a risk of developing specific diseases in the future.

MicroRNA analysis

MicroRNAs will be identified with Illumina next-generation sequencing using the TruSeq Small RNA Sample Preparation kit (Illumina) which allows for the addition of unique barcode sequences to each sample. Such barcoding allows pooling and simultaneous sequencing of multiple samples in a single-sequencing run on the Illumina NextSeq500 sequencer thereby significantly reducing the cost of sequencing. Pooling of multiple samples will generate adequate data amounts for detailed miRNA profiling, yet at limited costs. Data generated from the NextSeq500 sequencer will be filtered based on sequence quality as part of our established bioinformatics pipeline. This will also include matching the filtered data to annotated RNA databases such as miRNA sequences from miRBase (mirbase.org). The output from our bioinformatic pipeline will be quantitative miRNA expression levels for each sample, which will form the basis for a miRNA differential analysis where miRNAs with statistically significant expression changes will be found.

The microRNA (and extracellular vesicles) analysis is not a mapping of the genome. The microRNA profile is a snapshot of microRNA activity at the specific time of the blood sampling. Levels of microRNA are changing constantly and with the current knowledge on the topic it is impossible to predict a risk of developing specific diseases in the future. Cryotubes **not** used to for microRNA/exosome analysis will be destroyed.

Extracellular vesicle analysis

Extracellular vesicles (EVs, also known as exosomes) will be isolated from plasma samples before characterization of surface markers and content. EVs are isolated by a number of different

techniques, ultra-centrifugation, precipitation, size exclusion chromatography among others. While protein characterization will be done using classical molecular biological techniques such as ELISA and Western blots in addition to array techniques, EV-array, that utilizes a panel of antibodies directed against known EV surface markers. These analyses might be supported by proteomic analysis of all proteins as well as post-translational modifications such as phosphorylations and glycosylations. To broaden the feasibility of finding stroke type specific EV surface markers, we will utilize recombinant antibody library techniques to find novel disease binders with the potential of diagnosing stroke types in blood samples.

In addition, the nucleic acid (DNA and RNA including miRNA) content of EVs will be analyzed using next generation sequencing (NGS), qRT-PCR, and other nucleic acid detection techniques. Both the protein data and the nucleic acid data will be subjected to bioinformatic analysis using different pipelines and analysis tools depending on the dataset and the purpose of the analysis. A number of validated published databases will be used for annotation and comparison. EVs do not contain genomic DNA and the analysis are therefore not a mapping of the subject's genome. EV secretion and nucleic acid content in these are thought to change rapidly in the body due to external and internal signals and are considered a snapshot at the specific time of blood sampling. With the current knowledge on the topic it is impossible to predict a risk of developing specific diseases in the future.

Use of routine collected blood samples

The following biochemical entities will be used (lab results performed as a part of standard operating procedure): C-reactive protein, Glucose, HBA1c, Potassium, Natrium, Calcium, Albumin, Creatinine, eGFR (estimated Glomerular Filtration Rate), Total WBC (White Blood Cell count/Leukocytes), Hemoglobin, Erythrocytes, Erythrocytes (Volume Fraction, EVF), Erythrocytes distribution widths (RDW), Erythrocyte median cell volume (MCV), Hemoglobin concentration (MCHC and MCH), Reticulocyte count, Platelet count, Iron, Transferring, Ferritin, International Normalized Ratio (INR), Activated Partial Tromboplastin Time (APTT), Cholesterol (Total, HDL, LDL, Triglyceride).

Montreal Cognitive Assessment (MoCA)

The Montreal Cognitive Assessment (MoCA) is a brief screening tool originally designed to identify mild cognitive impairment. MoCA is a 1-page (healthcare administered), 30-point test, administrable in \approx 10 minutes, which evaluates different domains: visuospatial abilities, executive functions, short-term memory recall, attention, concentration, working memory, language, and orientation to time and space (appendix 4).

PASE - physical activity in the elderly

Participants will be asked to complete the physical activity in the elderly (PASE) questionnaire during the acute hospital admission. PASE is a 12-item questionnaire, which quantifies the amount of PA over a 7-day period. The PASE questionnaire was developed with the purpose of assessing the level of PA in middle-aged and elderly individuals. The PASE score is calculated by taking the average number of hours spent on an activity (sports, occupational activity, household activities, and leisure time activities) per day over a 7-day period multiplied by an activity coefficient. Item scores are added to reveal the PASE score. The score may range from zero to more than 400.

Remote Ischemic Conditioning questionnaire

In the RIC questionnaire the study participants are asked to reveal the level of discomfort (if any) experienced during the investigational treatment and whether they knew which treatment they received (Sham/Sham-RIC) despite the blinded study design. Control subjects will not be interviewed with the RIC questionnaire. The questionnaire is administered by study personnel. (Appendix 4)

5. Statistical analysis

Sample size estimation is based on yet unpublished data on elongation index in experimental stroke models. The maximum difference in IE between stroke and non-stroke (experimental models) was observed between 16 and 48 hours from stroke onset (IE of 0,43 and 0,58 at maximum deformability, 3000sm). Thus, a sample size of 12 stroke patients and 12 patients without stroke will be required to detect a deference of 0,15 on the elongation index with a power 90% (significance level 5%). To account for dropouts (estimated to maximum 3 per arm) and the additional study arm of RIC treated stroke patients a total of 45 patients will be included - 15 stroke patients (RIC), 15 stroke patients treated with sham-RIC and 15 patients (non-stroke controls). The maximum number of included patients will be 45.

Primary endpoint analysis

Differences in RBC deformability, RBC NOS3, plasma nitrite and other biomarkers over time (baseline, +2 hours and +7 days post RIC) between RIC groups (yes/no) will be examined using mixed models. Fixed effects in the model are RIC group, time, and the two-factor interaction between RIC and time. Subjects nested within RIC groups will be considered a random effect.

6. Ethical considerations

The RIC intervention is associated with mild to moderate discomfort and minimal risk for adverse events (10-12). The additional blood samples will however result in slight discomfort associated with venipuncture. The number of additional venipunctures will range from one to three, depending the number of routine planned blood samples. Every effort will be made to have study

blood samples taken when routine samples are taken. Use of sham is necessary for methodological reasons and is not associated with any risk/discomfort.

Advantages and disadvantages of participating in the study

- a. Potential advantages: Participants diagnosed with acute ischemic stroke will receive extra follow-up including an extra neurological examination.
- b. Potential disadvantages: mild/moderate discomfort and minor bleeding in the skin can occur on the RIC treated arm. The RIC treatment has otherwise proven safe and without serious adverse effects. Sham-conditioning will not cause discomfort or side effects. Extra blood withdrawals will cause discomfort for the patient.

Results from this pilot study will help establish whether a rheo-erythrocrine dysfunction in the RBC's is a biomarker for stroke and RIC. The establishment of a biomarker will help predict responders to RIC and serve as a preliminary investigation of a novel stroke biomarker and to better understand causes of microcirculatory dysfunction in stroke.

The pilot study will need approval from The Central Denmark Region Committees on Health Research Ethics and the Danish Medicines Agency before the research project begins.

7. Assessment of safety

Emergency unblinding procedure

All on call neurologists will have 24/7 telephone access to study investigators who can perform emergency unblinding if necessary. All changes will leave an audit-trail.

Adverse events

Patients are monitored in the stroke unit with NIHSS scoring and Scandinavian Stroke Scale (SSS) at close intervals, and adverse events are treated according to clinical guidelines.

During the acute in-hospital phase the patients will be asked if they have experienced any deterioration of health or new symptoms during or after treatment with the investigational device. Furthermore, all patients will have a 24/7 contact number to the stroke center and a contact to a study research physician and will be instructed to report any deterioration of health or new symptoms. All discharged patients (and relatives) will be given contact details to study personnel and be instructed to report any deterioration of health or new symptoms. The patients with acute ischemic stroke will once again be asked for adverse events at the interview on day 7. End of study is the interview on day 7.

Adverse events and adverse device events are defined according to ISO 14155:2011 and European Commission guideline on medical devices (MEDDEV 2.7/3 revision 3).

Adverse event (AE)

Any untoward medical occurrence, unintended disease or injury or any untoward clinical signs (including an abnormal laboratory finding) in subjects, users or other persons whether or not related to the investigational medical device.

Serious Adverse Event (SAE)

Adverse event that:

- a) led to a death, injury or permanent impairment to a body structure or a body function.
- b) led to a serious deterioration in health of the subject, that either resulted in: - a life-threatening illness or injury, or - a permanent impairment of a body structure or a body function, or - in-patient hospitalization or prolongation of existing hospitalization, or - in medical or surgical intervention to prevent life threatening illness.

Device Deficiency

Inadequacy of an investigational medical device related to its identity, quality, durability, reliability, safety or performance. This could be malfunctions, use error, or inadequacy in the information supplied by the manufacturer.

Adverse Device Effect

Adverse event related to the use of an investigational medical device. This includes any adverse event resulting from insufficiencies or inadequacies in the instructions for use, the deployment, the implantation, the installation, the operation, or any malfunction of the investigational medical device. This includes any event that is a result of a use error or intentional abnormal use of the investigational medical device.

Serious Adverse Device Effect (SADE)

Adverse device effect that has resulted in any of the consequences characteristic of a serious adverse event.

Unanticipated Serious Adverse Device Effect (USADE)

Serious adverse device effect which by its nature, incidence, severity or outcome has not been identified in the current version of the risk analysis report.

Anticipated SADE (ASADE)

An effect which by its nature, incidence, severity or outcome has been previously identified in the risk analysis report

Event report and causality assessment

The relationship between the use of the medical device and the occurrence of each adverse event will be assessed and categorized. All events will be registered in the electronic CRF and reported to the authorities at the interim analysis. A yearly safety report, containing a list of all SAEs/SADEs and near-miss incidents, thorough evaluation of individual events, risk/benefit analysis of the investigational medical device and safety conclusions, will be submitted to the Danish Health and Medicines Authority and the Independent Ethics Committee by the Sponsor as required by Danish law.

Exceptions to and special considerations about reporting procedures are stated below:

Acute stroke is an acute life-threatening disease with a high risk of neurological deterioration and mortality. The natural history of stroke is associated with a high risk of complications (stroke in progression, hemorrhagic transformation, dysphagia, cardiac arrhythmia, pneumonia, and other serious infections). These *complications* all relate to the index stroke (occurring *before* randomization) and is foreseeable. If an event occurs that based on the assessment by the investigator is a result of the natural history of the disease it will not be reported by the sponsor to the Danish medicines agency and regional ethics committee within 7 days/2 days (see list of foreseeable events/complications below).

All expected serious adverse events will be reported to the Danish Medicines Agency (and regional ethics committee) every 3 months.

All *new* serious events (Serious Adverse Events), complications that are not foreseeable or device near incidents or malpractice will be reported by the sponsor to the authorities (within 7 days, or 2 days if there is a risk of event reoccurrence) according to ISO 14155:2011 and European Commission guideline on medical devices (MEDDEV 2.7/3 revision 3). Investigators will report the event to sponsor (within 24 hours). Sponsor will as fast as possible and no later than 7 days, or 2 days if there is a risk of event reoccurrence, report the event to the Danish Medicines Agency and regional ethics committee.

All Serious Adverse Device Effect (SADE) will be reported to the Danish Medicines Agency (and regional ethics committee) within 7 days, or 2 days if there is a risk of event reoccurrence

List of foreseeable adverse events/complications

Foreseeable events/complications that will not be reported by the sponsor to the Danish Medicines Agency and Regional Ethics Committee within 7 days/2days.

Patient Population	Event	Frequency	Mitigation/treatment
TIA and AIS	Recurrent stroke.	10% at 90 days ^a	Standard medical treatment, intravenous thrombolysis/mechanical thrombectomy according to patient characteristics
AIS	Symptomatic intracerebral hemorrhage (related to IV tPA or EVT)	7% ^b	Antithrombotic/anticoagulation therapy cessation. Antifibrinolytic agent. Bloodpressure control.
AIS, ICH	Early (<24hours) and late (>24hours) neurological deterioration (Δ NIHSS \geq 2 or death)	7-22% ^c	According to etiology
AIS, ICH	Aspiration pneumonia	5-20% ^d	Antibiotic treatment according to hospital SOP

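### Section 5 analyses RBC deformability at day 7, but Table 2 schedules it only at baseline and +2 hours

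*Protocol*

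**What the plan says.** Section 2 (Primary endpoint) defines the endpoint as rheo-erythrocyte dysfunction with two named components: "deformability and Erythrocyte Nitric Oxide Synthase 3) will serve as a biomarker of the conditioning response".

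Section 5 (Primary endpoint analysis) fits mixed models to deformability, NOS3, plasma nitrite and other biomarkers "over time (baseline, +2 hours and +7 days post RIC) between RIC groups (yes/no"). The fixed effects are RIC group, time and their interaction. Deformability is the first marker listed, and no marker is exempted from any of the three times.

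Section 4, Table 2, has the row "RBC deformability X X", with marks under pre-allocation and +2h and none under +7days.

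The Blood samples text in section 4 says "Study blood samples will be drawn at the ward in a total of 3 times", that "Ektacytometry and flowcytometry will be performed on fresh whole-blood samples", and that "excess material (plasma) will be placed in a research biobank". The table of accepted time frames sets a window for the +7-day sample: "< 4 hours from completed 08 AM RIC". The deformability method takes "6 uL of heparinized or EDTA treated fresh blood".

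**The concern.** The analysis section needs three deformability readings per patient and the schedule provides two. The missing one is the only reading that could show what the full course of twice-daily conditioning does to this marker.

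This is more than an untidy table. Ward and laboratory staff can be expected to work from the schedule. A reading skipped on day 7 cannot be made later: ektacytometry uses fresh whole blood, the stored material is plasma, and section 7 makes the day-7 interview the end of the study. No later analysis plan can restore values that were never measured.

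**Working it through.** **Schedule against analysis.** Marks in Table 2, set beside the times named in section 5:

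| Item | Baseline | +2 h | +7 days |
|---|---|---|---|
| Table 2: blood samples | yes | yes | yes |
| Table 2: RBC deformability | yes | yes | **no** |
| Table 2: RBC erythrocyte dysfunction | yes | yes | yes |
| Table 2: biobank samples | yes | yes | yes |
| Section 5: deformability model | yes | yes | yes |

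Deformability is the only blood assay row without a day-7 mark.

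**Inputs.** 15 RIC and 15 sham patients (section 3); at most 3 dropouts per arm (section 5). The plan's own additions agree: 12 + 3 = 15 per arm and 3 × 15 = 45 in total. The calculation behind the 12 per group compares stroke with non-stroke and does not bear on this point. The 15 non-randomised controls are left out of the counts below.

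**Readings lost in the randomised arms if Table 2 is followed.**
- All 30 patients: 30 × 3 = 90 planned; 30 × 2 = 60 taken; 90 − 60 = 30 lost (33%).
- 12 completers per arm, counting dropouts as giving no readings: 24 × 3 = 72 planned; 24 × 2 = 48 taken; 72 − 48 = 24 lost (33%).

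**Effect on the model.** The interaction has (groups − 1) × (times − 1) degrees of freedom.
- Three times: (2 − 1)(3 − 1) = 2.
- Two times: (2 − 1)(2 − 1) = 1.

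The model can still be fitted, but it answers a narrower question: the change from baseline to +2 hours.

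**Treatment received at the last reading.** The regimen is one baseline session plus two a day for 7 days: 1 + 2 × 7 = up to 15 sessions. The +2-hour sample follows the first of them.

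**Blood available on day 7.** EDTA drawn: 2 × 3.0 = 6.0 mL. One run of each fresh-blood assay takes 0.006 mL (deformability) + 0.5 mL (aggregation and shear stress) + 0.05 mL (flow cytometry) = 0.556 mL, and 0.556 / 6.0 = 9.3%. The protocol does not state how much plasma the biobank needs. However, every sample set contains the same tubes, and at baseline and +2 hours that set already has to serve all the assays, deformability included.

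**The case against.** The strongest reply is that the rest of the protocol already settles the matter. Blood is drawn three times with the same tubes, ektacytometry is assigned to the fresh samples with no exception for the third draw, a day-7 window is given, and section 5 analyses day 7. Against that stands one empty cell in a table read from PDF by a program. Harm follows only if the laboratory receives fresh blood on day 7 and leaves out ektacytometry because of that cell. Even then, NOS3 is measured at day 7, a two-time-point deformability analysis remains, and neither the hypothesis nor the sample size names a day-7 target.

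Much of this stands. The blank is probably a slip, and the harm is conditional. A mark lost in reading the PDF cannot be fully excluded, but it is unlikely: the row keeps its cell structure and the neighbouring rows keep their day-7 marks. The loss also does not touch NOS3. Plasma nitrite has no row of its own in Table 2, but the text assigns it to the stored plasma, and biobank samples are marked on day 7. The counts above show how much data would be missing; they are not a calculation of lost power.

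The reply does not remove the contradiction. The text that points to day 7 does not amend the schedule, and the surviving markers do not supply the day-7 deformability comparison that section 5 promises.

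**Conclusion.** The concern holds: the protocol is wrong as written. Table 2 and section 5 contradict each other on a named component of the primary endpoint, and the difference must be settled before the schedule is used.

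The size depends on Table 2 being followed. In that case one third of the planned deformability readings in the randomised arms is lost (30 of 90, or 24 of 72 with maximum dropout), no day-7 value exists, and the effect of the seven-day course on deformability cannot be estimated. If staff follow the text instead, nothing is lost. The conclusion assumes that the blank cell is in the protocol itself, which a look at the source table will confirm.

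**What to change.** Add the +7 days mark to the RBC deformability row of Table 2, using the EDTA blood already drawn at that visit. The cost is one mark and about 24 to 30 more ektacytometer readings in the randomised arms, with no extra venipuncture.

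If day 7 was left out on purpose, change section 5 to say that the deformability model uses baseline and +2 hours only, and that the effect of the seven-day course is assessed on NOS3 and nitrite. That costs one sentence, but it gives up the day-7 comparison for deformability.
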